13.5 Trial Assessments & Data

OMWQ-HN

The OMWQ-HN is an oral mucositis-specific questionnaire [16] consisting of 9 items that assess impact of OM on a patient's well-being and oral functions. It will be administered by the research nurse and will take approximately 5 minutes to complete (Appendix 1). The patient will be asked to complete the questionnaire whilst they are at their research visit. Question 1 describes mouth and throat soreness using a 5-point scale, with 0 indicating no soreness and 4 indication extreme soreness. If the patient scores 0 on this first question, they should stop and not proceed to any futher questions. The second question is made up of five items, addressing the impact of mouth and throat soreness on patient function, with each item being scored on a 5-point scale with 0 indicating the function is not limited and 4 indicating the patient is unable to do the function. The remaining 3 questions assess the degree of mouth and throat pain and soreness using an 11- point scale, with 0 indicating no pain or soreness and 10 indicating the worst pain or soreness imaginable.

WHO Mucositis Oral Toxicity Scale

The World Health Organisation has developed a grading system for mucositis [17] (Appendix 2) which measures objective, subjective and functional aspects of OM based on clinical appearance and

functional status. The score is collected by the clinician and will take no more than a few minutes to complete.

• MD Anderson Dysphagia Inventory (MDADI)

The MDADI [18] (Appendix 3) is patient-reported swallowing outcome measure, specifically designed for the HNC population. Patients will be given the 20-item written MDADI questionnaire to complete at their research visit. The assessor will be available to help should the patient require assistance, but will not direct any answers. It will take approximately 10 minutes to complete. Each item on the MDADI follows a five-point response scale. Five scores can be calculated from the MDADI including 2 summary scores (global, total/composite) and 3 subscales (emotional, functional, physical) each calculated as a weighted average with a range of 20 (worst impairment) to 100 (no impairment). The 19-item total (or composite) score will be used to summarize overall impairment on the basis of physical, functional, and emotional domains.

• EORTC QLQ C30 (version 3.0), EORTC QLQ C30/H&N 35 (version 3.0) and EQ-5D-5L

The EORTC quality of life questionnaire is an integrated system for assessing the health-related quality of life (QOL) of cancer patients participating in clinical trials. There is a set of core questions (QLQC30) [19], supplemented by a HNC specific module (H&N 35) [20]. H&N 35 is a diagnosis-specific module designed to be used in conjunction with the QLQ-C30 and is intended for use among a wide range of HNC patients, varying in disease stage and treatment modality. The QLQ-C30 comprises five functional scales, three symptom scales, a global health status / QoL scale, and six single items. All of the scales and single-item measures range in score from 0 to 100 and high scale score represents a higher response level.

The EQ-5D-5L [21] consists of 2 pages – the EQ visual Analogue scale (EQ VAS) and EQ-5D-5L descriptive system. Responces to the EQ-5D-5L descriptive system will be converted into utility weights using an algorithm (anchored at full health (1) and dead (0)) facilitating the calculation of QALYs that are used to inform economic evaluations of health care interventions. A utility scores can range from 1 to -0.281 (for the worst health state, 55555).

Patients will be given the written EORTC QLQ-C30, H&N35 and EQ-5D-5L questionnaire (Appendix 4) to complete independently, at their research visit. The assessor will be available to help should the patient require assistance, but will not direct any answers. Patients are asked to reflect on their symptoms, functioning and quality of life over the previous week. The questionnaire takes approximately 15 minutes [22].

Performance Status Scale's (PSS-HN)

The PSS-HN [23] is a 3-item scale designed to evaluate functional performance of H&N cancer patients, specifically Normalcy of Diet, Eating in Public, and Understandability of Speech. The PSS-HN will be rated by health professionals including speech and language therapists, clinical nurse specialists and research nurses. The person collecting these data will remain consistent as far as is feasible, throughout the course of the trial. It will take approximately 5 minutes to complete.

Weight and Body Mass Index (BMI)

Weight and BMI will be performed as part of standard care and will be recorded by the research nurse for the trial.

Timed water swallow test (WST)

The WST [24] provides an indication of overall swallowing performance. It will be conducted unless deemed not appropriate or unsafe by the managing clinician. It will not be performed in patients who must remain nil by mouth, who will automatically score 0 for the test. If there are overt signs of significant aspiration (explosive coughing, prolonged coughing) or the patient is becoming distressed, the assessment will be stopped and the remaining amount in the cup measured and recorded. Measures of swallow capacity (mls/time) and swallow volume (mls/number of swallows) are derived from the data. Non-completion of the test will be recorded.

The WST will be conducted by speech and language therapists or a research nurse trained by a speech and language therapist, with reliability checks on 10 volunteers. The person conducting the WST at each centre will remain consistent throughout the course of the trial, as far as is feasible. It takes approximately up to 3 minutes to complete in this patient population.

• Qualitative Interviews:

Interviews with patients and health professionals will be conducted by an experienced qualitative researcher with skills in interviewing vulnerable populations around sensitive topics. A topic guide will be developed from discussions with the wider team, including the patient panel, from normalisation process theory (NPT)³⁰ and from literature around trial participation. The topic guide will be used in the interviews but interviewees will be encouraged to speak freely about any other issues relating to the pilot feasibility trial. The guide will be revised as new issues emerge in each interview. Each interview is expected to last between 20 and 40 minutes.

13.6 Trial Assessments

Baseline Assessments:

The following assessments must be conducted/administered at the (C)RT planning visit(s) - after the point of consent) but before day 1 of LLLT treatment.

- OMWQ-HN
- MDADI
- EORTC QLQ C30 (version 3.0), EORTC QLQ C30/H&N 35 and EQ-5D-5L
- WHO Mucositis Toxicity Scale
- Performance Status Scale's (PSS-HN)
- Timed water swallow test
- Recording of weight (weight/BMI)
- Use of analgesics and topical treatment

Assessment on Weeks 1-5 of LLLT treatment (inclusive)

Weekly assessments at weeks 1-5 of treatment, conducted/administered once each week. These will be conducted on the same weekday each week as day 1 of LLLT for the following 5 weeks (+/- 2 days to allow for local hospital variation of their weekly clinic review), before LLLT is given that day:

- OMWQ-HN
- Performance Status Scale's (PSS-HN)
- Recording of weight (weight/BMI)
- WHO Mucositis Toxicity Scale

Week 6 Assessment of LLLT Treatment (+/- 1 week)

Primary outcome assessments at week 6, conducted/administered once in week 6, on the same weekday as day 1 of LLLT (+/- 2 days to allow for local hospital variation of their weekly clinic review), before LLLT is given that day:

- OMWQ-HN -1, +2weeks for completion
- MDADI -1, +2weeks for completion
- WHO Mucositis Toxicity Scale
- Performance Status Scale's (PSS-HN)
- EORTC QLQ C30 (version 3.0), EORTC QLQ C30/HNC 35 and EQ-5D-5L -1, +2weeks for completion

- Timed Water Swallow test
- Recording of weight (weight/BMI)

The following information will also be recorded/collected at day 1 of LLLT, and weekly during weeks 1-6 of treatment:

- Use of analgesics and topical treatment
- Hospital admissions and interruptions in treatment (from week 2 of treatment)
- Quantity of enteral nutrition consumed, number of days of feeding tube in situ.
- Adverse events will be collected and concomitant medications checked and recorded on the eCRF
- Resource use associated with treatment will be collected via the CRF (e.g. staff involved and time associated with the delivery of the intervention, equipment costs etc.)

Week 12 (+/- 1 weeks) Head and Neck Follow-up visit (at the standard care visit)

 Adverse events will be collected and concomitant medications checked and recorded on the eCRF

Month 4 (+/- 2 weeks) Head and Neck Follow-up visit (at the standard care visit)

- OMWQ-HN
- MDADI
- WHO Mucositis Toxicity Scale
- EORTC QLQ C30 (version 3.0), EORTC QLQ C30/H&N 35 and EQ-5D-5L
- Performance Status Scale's (PSS-HN)
- Recording of weight (weight/BMI)
- Timed water swallow test
- Health Care Utilisation Questionnaire (including use of primary, secondary and social health care services and time away from usual activities)

Month 14 (+/- 2 weeks) Head and Neck Follow-up assessment (at the standard care visit)

- MDADI
- EORTC QLQ C30 (version 3.0), EORTC QLQ C30/H&N 35 and EQ-5D-5L
- Performance Status Scale's (PSS-HN)
- Timed water swallow test
- Recording of weight (weight/BMI)
- Health Care Utilisation Questionnaire

• Time and travel questionnaire

The following data will also be recorded at month 14:

- Recurrence, disease progression, death
- Feeding tube use (stopping)

Qualitative Sub-study:

- Patient interviews: 1-2 weeks after the recruitment discussion, and at approximately 4 months or 14 months (maximum of 2 interviews per patient).
- Staff interviews: staff may be contacted at any point during the LiteFORM trial
- Audio-recordings: each recruitment/consent discussion with patients for the LiTEFORM trial
- Observations: launch meeting, site initiation visits and all trial training sessions

13.7 Schedule of Events

Procedures	Patient Visits to Clinic								
	Pre- Screening	Screening & Planning visit (+1 week)	Weeks 1 to 5 of CRT Treatment (or as per standard care pathway)	Week 6 of CRT (+/- 1 week)	12 week follow up visit (+/- 1 week)	4 months (+/- 2 weeks)	14 months (+/- 2 weeks)		
Patient Information Sheet	٧								
Informed consent		٧							
Eligibility Confirmed		٧							
Demographics/ Medical History		٧							
Randomisation		٧							
MDADI		√*		V		٧	٧		
EORTC QLQ C30		√*		٧		٧	٧		
EORTC QLQ C30/H&N 35 (HN Cancer Module)		٧*		٧		٧	٧		
EQ-5D-5L		√*		٧		٧	٧		
OMWQ-HN		V*	√ (Weekly on day 1 of LLLT, +/- 2 days)	V		٧			
Performance Status Scale's		√ *	√ (Weekly on day 1 of LLLT, +/- 2 days)	٧		٧	٧		

Recording of Weight/BMI	٧*	√ (Weekly on day 1 of LLLT, +/- 2 days)	٧		٧	٧
Recording of Analgesics/Topical Treatments	٧*	√ (Weekly on day 1 of LLLT, +/- 2 days)	٧			
WHO Mucositis Toxicity Scale	٧*	√ (Weekly on day 1 of LLLT, +/- 2 days)	٧		٧	
Recording of Hospitalisation		v (From week 2: weekly on day 1 of LLLT, +/- 2 days)	٧			
Timed Water Swallow test	٧*		٧		٧	٧
(C)RT		√ (as per standard care)	√ (as per standard care)			
LLLT/LLLT sham		V (3 sessions per week from day 1 CRT – minimum 24 hrs between sessions)	V 3 sessions per week from day 1 CRT – minimum 24 hrs between sessions)			
Collection of Clinical outcomes		√ (weekly)	٧			٧
Health Care Utilisation Questionnaire					٧	٧
Time and Travel Questionnaire						٧
Adverse event assessments and Conmeds		√ (corresponding with LLLT sessions)	√ (corresponding with LLLT sessions)	٧		

^{*}Must be done after consent and prior to the first laser therapy session.

Version 2.1 dated 31/05/17

13.8 Withdrawals and Drop Outs

Participants have the right to withdraw from treatment or follow-up in the trial at any time without having to give a reason. Site teams should try to ascertain the reason for withdrawal and document this reason within the eCRFs and participant's medical notes.

The Principal Investigator may discontinue an individual's participation in the trial at any time if the Investigator considers it necessary for any reason including:

- Symptomatic deterioration
- Participant withdrawal of consent
- Significant protocol deviation or non-compliance
- Investigator's discretion that it is in the best interest of the participant to withdraw
- An adverse event that requires discontinuation of the trial intervention or renders the participant unable to continue in the trial
- Termination of the clinical trial by the sponsor
- Reported pregnancy

All patients who withdraw from treatment will be invited to continue follow up according to the trial protocol. Patients who withdraw consent for further follow up will be included in the analyses up to the date of withdrawal.

Separate consent will be obtained for interview participation, therefore participants are free to refuse to participate in the interview when contacted and those who choose to participate have the right to withdraw from or stop the interview at any time without having to give a reason.

Drop out:

A maximum participant dropout rate of 20% has been used when calculating the target sample size. It is estimated to be 10-15% based on data from previous trials and will be monitored by the independent DMC.

13.9 Storage and Analysis of Samples

No patient samples will be taken or used during this trial.

13.10 End of Trial

The last patient last contact will be at the 14 month follow up head and neck visit. The trial will be considered as closed at the time of database lock (expected around July 2020). The data will then be analysed, the trial report completed and results made available to the funder.

14. TRIAL INTERVENTIONS

14.1 Name and Description of Interventions

The LX2 Laser is indicated for use for OM and will be supplied by the manufacturer along with photo medicine approved glasses which must be worn by the practitioner, all observers and the patient whilst the laser is in operation.

Patients will receive LLLT plus standard care or sham LLLT plus standard care 3 times weekly by a non-contact method for a period of 6 weeks (from day 1 of (C)RT dose). LLLT will be administered ideally within 2 hours, but always before (C)RT session, with a minimum of 24 hours between each of the 3 laser therapy sessions. Each session will last 20-30 minutes, with LLLT at 6 pre-determined anatomical sites in the oral cavity.

LLLT will be delivered to the patient by nurses, allied healthcare professionals or delegated staff at a convenient time before the (C)RT treatment session (within an hour of the CRT dose). All patients will also receive the standard care offered for OM by each centre. Standard care varies across NHS Trusts but typically consists of oral hygiene instruction, topical analgesics and coating gels.

It is possible that a (C)RT session may be missed due to reasons such as an infection or the patient being unable to attend that visit. The LLLT will be delivered at the next session that the patient is able to attend for their (C)RT treatment as long as a minimum of 24 hours has passed, however data will still be collected wherever possible, particularly if the patient is an in-patient in the hospital.

Low Level Laser Therapies are available to the public for health and cosmetic treatments. LLLT equipment is CE marked and commercially available. Agreement has been obtained from the supplier to provide the specially modified sham treatment equipment to all sites for the purposes of this trial. The equipment will be serviced annually. Low level lasers are classed as 3b lasers, meaning they do not cut or burn but may injure the eye.

14.2 Schedule & Modifications

The LLLT will be a red laser, wavelength 660nm, power output 75mW beam area 1.5cm2, irradiance 50mW/cm2, exposure time 60 seconds, fluence 3J/cm2 per spot.

14.3 Concomitant Medications & Therapies

Laser therapy is contra-indicated for use over any known primary or secondary lesions. In line with manufacturer safety advice, the laser can be used on patients on low dose steroids but not on patients who are taking other immune suppressant drugs.

The laser can be safely used on patients with a pacemaker. The laser will only be used in the oral cavity for this trial.

Recent studies have shown no known adverse effects of LLLT in the parameters used for oral mucositis [25] and no issues with safety or tolerance and no survival difference at 18 months [26]. It the event that patients experience persistant or severe reactions to the laser therapy, the laser therapy must be discontinued immediately.

14.4 Assessment of Compliance

LLLT will be delivered by trained staff who will record the details of each session in the patient medical notes, including any sessions not attended. Operators of the laser will be required to complete a checklist of the intervention process, including number of doses administered and site of dose. Each staff member will also be required to document that the patient glasses and staff safety glasses were worn for the duration of the treatment and any occurrences of un-blinding. Compliance for the LLLT sessions will be monitored by the Trial Management Group using the online database using for data capture as well as reviewing source data at site visits.

Completion of trial assessments will be reported to the independent Data Monitoring Committee for discussion at the DMC meetings. The distribution of response times for questionnaires will be reported and agreed with the external DMC.

Prospective, planned deviations or waivers to the protocol are not allowed under the UK regulations on Clinical Trials and must not be used.

15. SAFETY REPORTING

15.1 Definitions

Term	Definition							
Adverse Event (AE)	AE) Any untoward medical occurrence in a participant, including occurrences which are not necessarily caused by or related to the intervention under trial.							
Adverse Reaction (AR)	An untoward or unintended response in a participant to which is related to the intervention under trial i.e. that a causal relationship between the trial intervention and an AE is at least a reasonable possibility and the relationship cannot be ruled out.							
	All cases judged by either the reporting medically qualified professional or the Sponsor as having a reasonable suspected causal relationship to the trial intervention qualify as adverse reactions.							
Serious Adverse Event (SAE)	 Results in death Is life-threatening* Requires inpatient hospitalisation or prolongation of existing hospitalisation Results in persistent or significant disability/incapacity Consists of a congenital anomaly or birth defect Other important medical events that jeopardise the participant or require intervention to prevent one of the above consequences * - life-threatening refers to an event in which the participant was at 							
	immediate risk of death at the time of the event; it does not refer to an event which hypothetically might have caused death if it were more severe.							
Serious Adverse Reaction (SAR)	An adverse event that is both serious and, in the opinion of the reporting Investigator, believed with reasonable probability to be due any dose of the trial intervention, based upon the information provided.							
Unexpected Serious Adverse Reaction (USAR)	A serious adverse reaction, the nature and severity of which is not consistent with the known information about the intervention under trial.							

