15.2 Recording and Reporting AEs, SAEs and SARs

AEs: All AEs that occur from day 1 of laser therapy up to and including the 12 week follow up visit (+/- 1 week) must be recorded on the eCRFs and in the patient medical notes.

The Principal Investigator is responsible for managing AEs at site according to the protocol. Seriousness and relation of the AE to the LLLT treatment should be assessed by the site PI. The Newcastle CTU will maintain a detailed central record of all AEs that occur. There is no requirement to inform sponsor of individual AEs.

SAEs and SARs: All SAEs that occur from day 1 of laser therapy up to and including the 14 month follow up visit (+/- 2 weeks) must be reported to the CI, Newcastle CTU and Sponsor immediately but no later than 24 hours of the site learning of its occurrence. Death should be reported as an SAE if it occurs within this period. If a death occurs after the 14 month visit it does not require reporting as an SAE but must still be recorded in the patient medical notes and eCRFs.

All SARs that occur from day 1 of laser therapy up to and including the end of study, as defined in section 13.10 must also be reported. SARs should be reported using the same process as for SAEs.

The initial SAE report will be made by the site PI completing the agreed SAE form which is sent via SOHO66 (secure fax to email system) to the Senior Trial Manager, Trial Manager, CI and nominated sponsor contact. The initial report can if necessary be made to the Clinical Trials Unit by telephone or e-mail and followed up formally using the SAE form. In the case of incomplete information at the time of initial reporting, or follow up information, a new SAE form must be completed and sent via secure system as soon as possible.

Contact details for reporting SAEs:

Trial Manager, Newcastle Clinical Trials Unit
[name], [contact] [name]

Please send the completed and signed SAE form(s) using the SOHO66 secure network

FAO LITEFORM TRIAL MANAGER to: TBC

All SAEs must be assessed for expectedness using the list of expected adverse events in LiTEFORM Protocol **section 15.2.1** and receive full review by the PI at site and discussed with the CI. It is encouraged that the CI consults with the Chair of the TSC and DMC.

For each SAE the following information will be collected:

• Full details in medical terms and case description

• Event duration (start and end dates, if applicable)

Action taken

Outcome

Seriousness criteria

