Causality in the opinion of the PI

Whether the event is considered expected or unexpected.

Any change of condition or other follow-up information should be faxed to the Newcastle CTU as soon as it is available or at least within 24 hours of the information becoming available. Events will be followed up until the event has resolved or a final outcome has been reached.

Expected AE/ARs:

Most adverse events that occur in this trial, whether they are serious or not, will be related to the (C)RT that the patient is receiving as part of their standard care and not related to delivery of the LLLT.

The following are AEs that could be reasonably expected to occur in this population of patients who are undergoing (C)RT for HNC. It is expected that patients receiving primary or adjuvant radiotherapy \pm chemotherapy for head and neck cancers may require admission for symptom control of the following:

- Mucositis
- Dysphagia
- Pain
- Nausea and vomiting
- Weight loss
- Poor oral intake
- Infection
- Fatigue
- admission for hydration and/or feeding via NGT or Radiologically Inserted
 Gastrostomy (RIG) if the patient has one in situ

Patients may also experience tinnitus (chemotherapy related) and anaemia, although may not require admission for these symptoms.

15.2.1 Expected AEs after receiving LLLT:

- nausea
- dizziness
- increase in OM symptoms within 24 hours of receiving laser therapy
- decrease in OM symptoms within 24 hours of receiving laser therapy
- tingling sensation in the mouth
- feeling of warmth in the mouth

It the unlikely event that a patient experiences persistant or severe reactions to the laser therapy, the laser therapy must be discontinued immediately.

All occurrences of **expected** SAEs/AEs will be included in the first annual progress report but will not require completion of the SAE form or expedited reporting to REC. They must be recorded by the site on the eCRFs and in the patient notes. Treatment related AE and All SAEs will be reviewed by the DMC throughout the trial.

Coding:

AE's and SAEs must be coded using CTC version 4.0. SAEs will be recorded and reported according to category, severity (mild, mod, severe) and related-ness (definitely, probable, possible, unlikely, unrelated) to intervention.

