6. SAFETY

6.1 Adverse events

All adverse events (AEs) that occur from day 1 of laser therapy up to and including the 12 week follow up visit (+/- 1 week) must be recorded on the eCRFs and in the patient medical notes.

The severity of symptoms are graded using the Common Terminology Criteria for Adverse Events (CTC) 4.0. The CTC grades 1 through 5 with unique clinical descriptions of severity for each AE based on this general guideline:

- Grade 1: Mild; asymptomatic or mild symptoms; clinical or diagnostic observations only; intervention not indicated.
- Grade 2: Moderate; minimal, local or non-invasive intervention indicated; limiting age appropriate instrumental activities of daily living (ADL).
- Grade 3: Severe or medically significant but not immediately life-threatening; hospitalization or prolongation of hospitalization indicated; disabling; limiting self-care ADL.
- Grade 4: Life-threatening consequences; urgent intervention indicated.
- Grade 5: Death related to AE

Adverse events will be coded using the MedDRA dictionary and presented by preferred term, grouped by system organ class.

Treatment emergent adverse events, i.e. those that occur or worsen on or after first dose of study IMP, will be summarised by grade according to the worst grade experienced since day 1 of laser therapy. Data will also be presented separately for related (possibly, probably, definitely) and unrelated (unrelated, unlikely) events. The occurrence of non-serious adverse events will be tabulated, as required for EudraCT reporting. All data will be presented in the safety population by randomised treatment group.

Example Table 11: All adverse events by type: worst severity reported

	Laser (n =)	Sham (n =)
System Organ Class 1, n (%)		
Preferred Term		
Mild		
Moderate		
Severe		
Life-threatening consequences		
Death		
Total number affected		
Preferred Term		
Mild		
Moderate		
Severe		
Life-threatening consequences		
Death		
Total number affected		
System Organ Class 2, n (%)		
Preferred Term		
Mild		
Moderate		
Severe		
Life-threatening consequences		
Death		
Total number affected		

Example Table 12: Non-serious adverse events by type: worst severity reported (unrelated and unlikely causality)

	Laser (n =)	Sham (n =)
System Organ Class 1, n (%)		
Preferred Term		
Mild		
Moderate		
Severe		
Life-threatening consequences		
Death		
Total number affected		
Preferred Term		
Mild		
Moderate		
Severe		
Life-threatening consequences		
Death		
Total number affected		

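### Protocol 15.1 sets a higher causality threshold and fewer judges for a serious adverse reaction than for an adverse reaction, so a serious unexpected reaction can miss USAR classification

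*Protocol*

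**What the plan says.** Protocol 15.1 holds three linked definitions.

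- **Adverse reaction.** The test is that "a causal relationship between the trial intervention and an AE is at least a reasonable possibility and the relationship cannot be ruled out". Two parties can make that judgement: "All cases judged by either the reporting medically qualified professional or the Sponsor as having a reasonable suspected causal relationship" qualify.
- **Serious adverse reaction.** The event must be serious and, "in the opinion of the reporting Investigator, believed with reasonable probability to be due any dose of the trial intervention".
- **USAR.** This is "A serious adverse reaction, the nature and severity of which is not consistent with the known information about the intervention under trial".

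Protocol 15.2 has SAEs graded by "related-ness (definitely, probable, possible, unlikely, unrelated) to intervention" but does not say which grades make an event a reaction. It also sets two reporting windows. SAEs are reportable up to the month-14 visit. The later window covers "All SARs that occur from day 1 of laser therapy up to and including the end of study".

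Under Protocol 15.3, USARs go to the ethics committee within 15 calendar days and principal investigators are told of them. SAP 6.1 puts the dividing line lower on the scale, with events shown as "related (possibly, probably, definitely") against unlikely and unrelated.

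**The concern.** A SAR would normally be the subset of ARs that are serious. Here the step from AR to SAR changes two further things: possibility becomes probability, and the sponsor's judgement no longer counts. A serious event can therefore be an AR without being a SAR, and the protocol gives no reason for this.

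Expedited reporting hangs on the narrower term. An event that is not a SAR cannot be a USAR, and USAR status is what triggers the 15-day report and the notice to sites. The events exposed are those with real but unproven suspicion of a link to the laser, or with disagreement between site and sponsor.

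**Working it through.** There is no figure to reproduce, so the check sets the definitions side by side and follows example events through the reporting rules.

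| Term (Protocol 15.1) | Causality threshold | Who may judge |
|---|---|---|
| AR | reasonable possibility, not ruled out | reporting professional or sponsor |
| SAR | reasonable probability | reporting investigator |
| USAR | as SAR, because it is defined through SAR | as SAR |

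**Does another section restore the lower threshold or the second judge?**

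- Protocol 15.2 collects the principal investigator's opinion of causality for each SAE and nobody else's.
- Protocol 15.3 starts the site's escalation from an event already regarded as a SAR.
- Protocol 15.4 gives the chief investigator a causality role only where a local assessment could not be obtained. The sponsor's listed assessment task is expectedness.

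None of these gives the sponsor a stated route to upgrade causality for a serious event.

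**Three serious, unexpected events before the month-14 visit, read literally:**

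1. Investigator rates it probable. It is an AR, a SAR and a USAR, and is reported within 15 days.
2. Investigator rates it possible. It meets the AR test and falls in the related group of SAP 6.1. It can fail the SAR test, in which case it is not a USAR and Protocol 15.3 requires no report.
3. Investigator rates it unlikely but the sponsor suspects a link. The sponsor's judgement makes it an AR. It is not a SAR, because only the investigator's opinion counts there, so it is not a USAR.

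In cases 2 and 3 the event is still sent as an SAE to the chief investigator, trials unit and sponsor within 24 hours (Protocol 15.2), and the DMC reviews all SAEs. What is missing is the classification and the expedited report.

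**The same events after the month-14 visit.** The SAE duty has ended and the SAR duty runs on to the end of study, which Protocol 13.10 places at database lock. Cases 2 and 3 then have no reporting route. A death would still be entered in the notes and eCRF, but not reported as an SAE.

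**The case against.** The strongest reply is that this is loose drafting with little practical effect. Much of that stands.

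- The protocol maps possible to neither threshold. A site may treat a possible rating as enough for a SAR, so case 2 can be missed but need not be. Case 3 does not depend on this mapping.
- Before month 14 the safety nets are real: 24-hour SAE reporting, DMC review of all SAEs, and DMC access to unblinded data (Protocol 13.4). The relief from the SAE form in Protocol 15.2.1 covers expected events only, so it does not touch USAR candidates.
- The gap after month 14 is narrow for those who have that visit, since it is the last planned contact and no later visit would elicit events.
- The protocol supplied is version 2.1 and the SAP cites version 4.0, so section 15.1 may since have changed. The conflict between AR and SAR lies within one version; only the comparison with SAP 6.1 crosses versions.

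A reader might also infer more than the documents support.

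- **That non-serious events have a lower threshold than serious ones.** The AR definition is not limited to non-serious events. The fault is that two overlapping definitions disagree about the same serious event.
- **That an effect on tumour behaviour, which Protocol 8.1 calls plausible, would be filtered out.** Recurrence, progression and death are recorded at month 14 whatever the causality rating (Protocol 13.6), and all deaths go to the DMC (Protocol 15.5). Such an effect would be sought by comparing arms, not in one blinded investigator's rating.
- **That the final report will conflict with the SARs reported.** SAP Tables 12 to 14 split causality for non-serious events only. Serious events are listed in Table 15 with the raw rating, so those rated possible stay visible.

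**Conclusion.** The point holds as an inconsistency within Protocol 15.1 that bears on expedited safety reporting. A serious unexpected event can satisfy the AR definition and still escape USAR classification, the 15-day report and notice to sites. After the month-14 visit it can escape reporting altogether. Up to that visit it is captured and reviewed.

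The size cannot be given. The documents report no count of serious events and no distribution of causality ratings among the 87 participants randomised (SAP 2.6). The events at risk are the serious, unexpected ones rated possible or suspected only by the sponsor, and the documents do not support an estimate of what share of serious reactions that would be.

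The conclusion rests on a literal reading of the SAR wording and on section 15.1 standing as in version 2.1. It does not touch the efficacy analysis or the planned safety tables. It is worth correcting because a stated rule can misclassify serious reactions and one definition cures it.

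**What to change.** - In Protocol 15.1, define a SAR as an adverse reaction, as already defined there, that meets any seriousness criterion. This brings in the same threshold and the same judges, investigator or sponsor.
- Carry the definition into the USAR rules in 15.3, and add the sponsor's causality judgement to the SAE data in 15.2 and the responsibilities in 15.4, so that it can take effect.
- State beside the relatedness scale in 15.2 that possible, probable and definite count as related, in line with SAP 6.1.
- Follow-up visits have ended (SAP 2.6 dates the last one 27 October 2019), so also recheck serious unexpected events against the AR definition before SARs and USARs are finally reported. Table 15 of the SAP already lists causality and expectedness, which identifies those rated possible. Events suspected only by the sponsor need the sponsor's own review.

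The cost is one definition, its cross-references and a short review of the SAE listing. The downside is that a few more serious events will be classed as SARs.
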